#### 6.2 Interim Analysis Specification

An interim analysis is planned to formally assess the sample size calculation for this study. A designated unblinded statistician, independent from the study, will conduct the interim analysis when approximately 50% of the patients have reached the 12 month time point. The observed effect size at this interim time point will be estimated for analysis, spending 0.001 of the overall alpha-level of 0.05. This leaves 0.049 alpha for the final analysis. This is appropriate, as the study Sponsor is not expecting statistical significance, nor planning to stop the study, only to re-assess the sample size calculation. Furthermore, the effect of sample size adjustment through interim analysis has been shown to have negligible effect on Type I error rates [21].

The observed effect size at the interim time point will be used by the independent, unblinded statistician to re-calculate the sample size for the study. The effect size will not be shared with the Sponsor, only whether or not an increase in the sample size is warranted. The independent, unblinded statistician will only report to the Sponsor the sample size required for 80% and 90% power given the data to that point.

If the initial sample size is large enough to provide a minimum of 80% power (i.e.  $n \ge n^*$ ), the trial will continue until all the planned number of subjects (*n*) are recruited. Otherwise, if  $n < n^*$ , we will increase the sample size and the trial will continue until enough patients (*n*\*) have been recruited that the desired power is achieved. The final new sample size for is

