# 4.2 Primary Outcome

The primary objective of this study is to determine whether nSTRIDE APS is superior to HA with respect to the improvement in mean WOMAC LK 3.1 pain score (change from baseline to 12 months post-injection). The primary hypothesis described below will be tested along with the secondary hypotheses listed in Section 4.3 using a conventional fixed-sequence procedure [11, 12], constructed using a pre-specified order of hypotheses. These tests will be performed at the 0.05 level. If the first null hypothesis is rejected, the second test will be performed at the 0.05 level. If the first null

hypothesis is not rejected, the second test, and all subsequent tests, will be performed as exploratory analyses. Since the order of the tests is fixed a priori, and the second hypothesis is tested only if the previous hypothesis has been rejected, the principle of closed testing implies that no adjustment to control the familywise error rate is necessary. The Fixed-Sequence Method is described as an acceptable method for addressing the multiplicity problem in Section IV.C.5 of the FDA draft guidance entitled, "Guidance for Industry – Multiple Endpoints in Clinical Trials".

A two-tailed independent sample T-test will be used to test the primary endpoint.

The hypotheses will be:

H0:  $\mu_{APS} = \mu_{Control}$ 

Versus

HA: µAPS ≠ µControl

A finding of nSTRIDE APS superiority on the WOMAC LK 3.1 Pain subscale will be considered evidence of nSTRIDE APS superior efficacy, and the device will be considered more efficacious than HA for the treatment of knee pain associated with OA at 12 months post-injection.

The impact of the usage of APS on function will be evaluated as part of the primary endpoint; however, no formal statistical test will be done as a part of the study success criteria. A qualitative assessment of the changes in WOMAC Function over time for APS and HA will be discussed, in order to ensure that the impact of the treatment on function is neutral or positive. The following descriptive analyses will be performed for this assessment of function:

- (1) A graphical examination of the changes in WOMAC Function for APS and HA over time, including means and standard error bars.
- (2) Descriptive statistics for the mean changes in WOMAC Function over time, separately for each treatment group. These will include mean, median, standard deviation, minimum, maximum, and 95% confidence intervals.

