#### 6.1 Sample Size

Data used to estimate sample size are from Zimmer Biomet study APSS-33-00, a randomized study comparing APS to saline in human subjects. This calculation assumes that hyaluronic acid will perform similarly to saline. Estimates of expected difference and pooled standard deviation from this study are shown in **Table 15**.

Group	n	Mean Improvement in WOMAC	St. Dev.	Mean Diff.	Pooled St. Dev.	Sample Size Each	Combined Plus 20% Attrition
		Palli				Group	
APS	30	7.20	3.25				
Saline	15	4.93	4.73	2.27	4.06	93	246

Table 15- Results from APSS-33-00

The calculation results in 93 per group. Results are based on a two-tailed alpha of 0.049 and statistical power of 90%.

Planned enrollment was increased to 123 per group to protect against attrition of approximately 25% in either treatment group.

<sup>1 Under the original sample size calculations, the sample size of 196 randomized (98 per group) was adjusted to accommodate potential dropout rate of approximately 20%, resulting in a total sample size of 246. This sample size

A maximum of 30 sites will participate in the study. Enrollment will be stopped at any site reaching a limit of 30% of planned study enrollment.

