#### $n_{new}=Max(n,n*).$

Therefore, if an increase in sample size is warranted by the re-calculation of the sample size requirements at the interim time point, it will only be reported how many more subjects are required in order to meet the study endpoint at

assumed a 2-sided alpha of 0.025 and power of 0.95. Note that, in accordance with the primary hypothesis, the sample size has been re-calculated under a 2-sided alpha=0.049 (instead of 2-sided alpha = 0.025) and a power of 0.90. This results in a sample size of 93 per group, or 117 when including 20% attrition and 124 when including 25% attrition. Thus the original sample size of 246 is sufficient for testing the primary endpoint with 90% power, and accommodate almost 25% attrition.

sufficient power. The sample size will not be reduced as a result of the sample size re-calculation. The sample size will only be increased, if the reassessment is so indicated. If the reassessment does not indicate an increase in sample size, then the study will continue as originally planned.

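### The sample size is reset from the unblinded interim effect with no stated cap or direction rule, and the ordinary t-test that follows has a type I error of up to about 7%, not 4.9%

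*SAP*

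**What the plan says.** SAP section 6.2 places the interim when about 50% of patients have reached 12 months and spends 0.001 of alpha there, leaving 0.049 for the final analysis. On the basis of the recalculation it says: "The observed effect size at the interim time point will be used by the independent, unblinded statistician to re-calculate the sample size". If the planned n gives less than 80% power, then "we will increase the sample size and the trial will continue until enough patients" (n*) are recruited, so the new size is Max(n, n*). It is never reduced: "The sample size will only be increased, if the reassessment is so indicated".

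The final test is in section 4.2: "A two-tailed independent sample T-test will be used to test the primary endpoint". No combination test, pre-fixed stage weights or adjusted critical value appears. The only protections offered are the 0.001 spend and the sentence "Furthermore, the effect of sample size adjustment through interim analysis has been shown to have negligible effect on Type I error rates".

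No maximum n is stated in the SAP or in the supplied protocol synopsis. No direction rule is stated either, though one phrase in section 6.2, "it will only be reported how many more subjects are required in order to meet the study endpoint", could be read as raising n only when APS leads. The nearest thing to a ceiling is in section 6.1: "A maximum of 30 sites will participate in the study" and "Enrollment will be stopped at any site reaching a limit of 30% of planned study enrollment". The protocol synopsis allows up to 15 centres.

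**The concern.** When the size of the second stage depends on the first-stage effect, the pooled t-statistic no longer has its usual null distribution. Whether the error rises or falls depends on where the increase happens. Raising n after a weak interim result dilutes it and gives a fresh chance to reject; raising n after a promising result slightly lowers the chance of rejecting under the null. The rule in section 6.2 makes its largest increases where the interim effect is smallest.

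This is the trial's confirmatory test and the gate to the fixed sequence of secondary tests in section 4.3. If its error rate is not the stated one, a finding of APS superiority is more likely to be false than the SAP claims. The defect cannot be credibly repaired once the interim effect is known.

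**Working it through.** **Inputs.** Final two-sided level 0.049, interim at half the information, 80% power target, size Max(n, n*), no stopping at the interim (all section 6.2); ordinary t-test (section 4.2); 1:1 allocation (section 1.3).

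**The SAP's own figure.** 0.001 + 0.049 = 0.05. With n fixed at plan, integration gives 0.0490 for the final test, or 0.0492 if an interim rejection at 0.001 also counts. The stated level therefore holds for a fixed-n design.

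**The rule as a formula.** Let z1 be the interim z-statistic and n1 the interim size per arm, so the planned size is 2·n1. The size giving 80% power at the observed effect satisfies

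n*/n1 = ((1.969 + 0.842)/|z1|)² = (2.810/|z1|)².

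n rises when this ratio exceeds 2, that is when |z1| < 2.810/√2 = 1.987. Under the null that happens in 95% of trials. The ratio is free of the SD and of whether 93 or 123 per arm is used.

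**Why the error moves.** With r = n_new/n1, the pooled test rejects for APS when the second-stage z exceeds (1.969·√r − z1)/√(r − 1).

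- z1 = 0.5, planned n (r = 2): threshold 2.284, conditional error 1.1%. At n* (r = 31.6): threshold 1.910, error 2.8%.
- z1 = 1.5, planned n: threshold 1.284, error 10.0%. At n* (r = 3.51): threshold 1.381, error 8.4%.

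Increases after weak interims add error and increases after promising ones remove some. This is why the type of cap matters.

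**Integrating over z1 under the null:**

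| Rule | Either direction, two-sided | n rises only if APS leads |
|---|---|---|
| No cap | 7.03% (false APS win 3.51%) | 5.96% (2.90%) |
| Truncated at 1.25× | 5.25% | 5.07% |
| Truncated at 1.5× | 5.50% | 5.20% |
| Truncated at 2× | 5.86% | 5.38% |
| Truncated at 3× | 6.27% | 5.58% |
| Planned n kept if n* > 1.25× | 4.86% | 4.88% |
| Planned n kept if n* > 1.5× | 4.81% | 4.85% |
| Planned n kept if n* > 2× | 4.72% | 4.81% |
| Planned n kept if n* > 3× | 4.69% | 4.79% |

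Simulating the actual t-test (400,000 null trials, 61 then 123 per arm) gives 7.02% and 5.96% without a cap, 5.89% truncated at 2×, and 4.75% with planned n kept beyond 2×.

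**Sensitivity, no cap, either direction.** Interim at 40% or 60%: 6.7% or 7.3%. 90% power target: 6.8%. Final test at 0.05 instead of 0.049: 7.16%, so the 0.001 spend buys 0.13 points.

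**Site limits read as a ceiling.** 15 × 0.30 × 246 = 1,107 subjects (4.5× plan); 30 × 0.30 × 246 = 2,214 (9×). Truncation there gives 6.6% or 6.8% (5.7% or 5.9% if only APS-leading increases count). Under the null, n* exceeds 4.5× when |z1| < 2.810/√9 = 0.937, in 65% of trials, and 9× when |z1| < 2.810/√18 = 0.662, in 49%. An unwritten limit would often decide the final n.

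**The case against.** The strongest reply is that 7.0% describes a trial nobody could run. It needs unlimited enrolment; the null median under the rule is about 1,080 per arm against 123 planned. With truncation at 1.5 to 2 times plan the error is 5.5% to 5.9%, and with the planned n kept beyond the cap there is no inflation. That stands: 7.0% is the figure for the text as written and sits at the upper end. It does not rescue the plan, because the SAP does not say which of these rules applies, and every truncating cap examined exceeds 5%.

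Second, the claim is about APS. In the APS-leads reading the 5.96% splits into 2.90% false APS wins and 3.07% false HA wins. Against 2.5% per side rather than 2.45%, the excess of false APS wins is 0.4 points uncapped and 0.24 points with truncation at 2×. This is fair, and that reading is clearly the milder one, but it is not the rule the SAP states.

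Third, the calculations are normal-theory without the imputation of section 6.3.1, so three-digit precision should not be read into them. Fourth, only the protocol synopsis was available and the reference cited for negligible effect was not, so what that source showed is not judged here. The conclusion follows from the SAP's own rule.

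**Conclusion.** The concern holds. As written, sections 6.2 and 4.2 give a two-sided type I error of about 7.0% (false APS win 3.5%), or 6.0% (2.9%) if increases happen only when APS leads, against a stated 4.9% (2.45%). The statement that the adjustment has negligible effect is wrong for this rule, and the 0.001 spend does not correct it. The figures assume an interim near half the information, an 80% target, normal outcomes and no stated cap. A cap alone does not settle the matter: truncation leaves inflation, while keeping the planned n beyond a cap of up to 4.5× does not. This must be fixed before interim data are unblinded.

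Two smaller points do not carry this conclusion. Section 4.2 tests at 0.05 while 6.1 and 6.2 use 0.049. Section 6.2 also describes the report to the sponsor in three ways, two of which let the absolute standardised effect be back-calculated: 150 evaluable per arm for 80% power implies 2.810 × √(2/150) = 0.32.

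**What to change.** State in section 6.2 a maximum n, whether n is truncated at it or left at plan beyond it, and whether n may rise when HA leads. Then adopt one of these:

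1. Keep the effect-based rule and test the primary endpoint with an inverse-normal combination of one-sided, APS-direction stage-wise p-values, weights √0.5 each, at two-sided 0.049. Fix stage membership at the interim cut, impute within stage, and use the same statistic in the tipping-point analysis. One-sided p-values matter: with two-sided ones, half of null rejections have the stages pointing in opposite directions. Early scores of second-stage patients must not inform n*. If those of 61 per arm did (assumed correlation 0.5 to 0.7 with the 12-month change), the error would be 5.2% to 5.5% with truncation at 2×.
2. Base n* only on the blinded pooled SD and the planned 2.27 difference, and keep the t-test at 0.049. Simulated error is 4.89% to 4.94% (2× cap, true SD 4.06 to 6.5).
3. Keep the effect-based rule and the t-test at 0.049, with a stated cap and no increase when n* exceeds it, and show the error (about 4.7% at 2×).

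Another route is acceptable if its error is shown to be at most 0.049, for example truncation at 2× with the t-test at about 0.040. In every case, replace the negligible-effect sentence with the calculated error of the adopted rule, align the primary test level in section 4.2, and give one description of the sponsor report that hides the effect, such as pre-set size bands.

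The cost is SAP wording, added analysis specification for option 1, a change in how the interim is run and reported, and possibly a different number recruited. No new data are collected. Power for an APS win (123 per arm, no attrition):

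| Design | d = 0.2 | 0.3 | 0.4 | 0.56 (planned: 2.27/4.06) |
|---|---|---|---|---|
| t-test, truncated at 2× (error inflated) | 56% | 87% | 97% | >99% |
| Option 1, truncated at 2× | 51% | 84% | 97% | >99% |
| Option 3 at 2× | 37% | 68% | 89% | 99% |
| No re-estimation | 34% | 65% | 88% | 99% |

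Option 1 loses about 5 points at d = 0.2 and essentially nothing at the planned effect. Option 3 is simplest but gives up most of the gain at small effects. Option 2 cannot respond to a smaller effect, and its blinded SD is slightly conservative: √(4.06² + 2.27²/4) = 4.22 if 2.27 is true, about 8% more subjects.

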### 1.3 Randomization

Subjects will be randomized to either the APS or HA treatment group on a 1:1 basis. The subjects and investigators will both remain blinded throughout Phase I of the study. Assignment to treatment groups will be stratified by site and will use random block sizes. Specifically, designated unblinded personnel at each site will provide the masked syringe to the injecting health care provider. To protect the double-blind, the treating health care professional and evaluating health care professional will be different individuals. Assignment will not be revealed until after the blood has been drawn for nSTRIDE APS Kit processing.

The randomization plan will be produced using SAS v 9.4 or similar software. Balanced randomization with random block sizes (1:1, APS: HA) will be implemented. In the event that, post-randomization, no study treatment was given, randomization will not be reassigned; however, this case will not count toward the overall sample size. Randomization will continue with the next case enrolled until the minimum sample size is reached in both treatment groups. Randomization will be stratified by site, and each site will receive separate randomization plans using random predetermined block sizes that will remain undisclosed to the sites. The randomization file will be uploaded into the electronic data capture (EDC) system. Once the subject is enrolled into the EDC and has been identified as eligible for randomization, the randomization allocation will be visible within the EDC and viewable only by the unblinded research associate. The subject will be treated according to the contents of the displayed randomization allocation.

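### SAP 6.2 gives three conflicting rules for what the sponsor is told after the unblinded interim, and any reported sample size discloses the magnitude of the effect that is meant to be withheld

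*SAP*

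**What the plan says.** SAP 6.2 has an independent, unblinded statistician re-calculate the sample size from the observed effect size when about half the patients have reached 12 months. It then states three rules for what leaves that statistician's hands:

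1. Second paragraph: "The effect size will not be shared with the Sponsor, only whether or not an increase in the sample size is warranted". This is a yes/no message.
2. The next sentence: the statistician "will only report to the Sponsor the sample size required for 80% and 90% power given the data to that point". This is two numbers, released whether or not an increase is needed.
3. Closing paragraph, after the formula for the new sample size: if an increase is warranted, only the number of additional subjects is reported; otherwise the study continues as planned.

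The decision rule itself is tied to 80% power. If the planned n gives at least 80% power, n stands; if not, the study recruits to n*, and the new size is the larger of n and n*. The text also calls the target the *desired power* and, in the closing paragraph, *sufficient power*, without defining either term.

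The remaining inputs to the calculation are also in the SAP. On alpha, 6.2 says "This leaves 0.049 alpha for the final analysis". On the test, 4.2 says "A two-tailed independent sample T-test will be used to test the primary endpoint". On allocation, 1.3 says "Subjects will be randomized to either the APS or HA treatment group on a 1:1 basis".

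**The concern.** The three rules release different amounts of information and cannot all be followed, so the independent statistician has no clear instruction. The second rule also defeats the first. With alpha, power, test and allocation fixed, the required n is a monotone function of the standardised effect, so anyone holding the SAP can invert it. The third rule has the same property whenever an increase is made.

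The SAP itself decided that the interim effect should be withheld. If the sponsor can work out its size while 12-month data on a patient-reported endpoint are still being collected, decisions about recruitment, retention or conduct may be influenced by it. An outside reader could then no longer rely on the stated confidentiality.

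**Working it through.** **Inputs.** Two-sided alpha 0.049 (SAP 6.1, 6.2); two-sample t-test (4.2); 1:1 allocation (1.3); power 80% or 90% (6.2); planning difference 2.27 and SDs 4.06 (pooled) and 4.73 (saline arm) from Table 15; attrition 15%, 20% or 25%, depending on the place (6.1 and its footnote, 6.3.1).

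**The plan's own figure.** Per group, n = 2 × (SD/difference)² × (z_alpha + z_power)², with z_alpha = 1.968 and z_90 = 1.282.
- SD 4.06: 2 × (4.06/2.27)² × 3.250² = 67.6, so 68 (69 by noncentral t). The stated 93 is not reproduced.
- SD 4.73: 92 (93 by noncentral t), which matches 93.
- The superseded 98 per group in the footnote (alpha 0.025, power 95%, SD 4.06) is reproduced: 97 by the normal formula, 98 by noncentral t.

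So the method agrees with the sponsor's. The mismatch at 93 is a separate matter and does not enter the inversion, which needs no SD.

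**Inversion.** Let d be the absolute standardised effect: d = sqrt(2/n) × (z_alpha + z_power). At 80% power the bracket is 1.968 + 0.842 = 2.810.
- n = 123 evaluable, 80%: sqrt(2/123) × 2.810 = 0.358 (noncentral t 0.360).
- n = 200 evaluable, 80%: sqrt(2/200) × 2.810 = 0.281 (noncentral t 0.282).
- n = 69 evaluable, 90%: sqrt(2/69) × 3.250 = 0.553 (noncentral t 0.557).

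**Precision.** At d = 0.30 the required n is 177 (80%) or 236 (90%). Inverting 177 returns 0.2995 to 0.3004; inverting 236 returns 0.2998 to 0.3005.

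**Are two values needed?** No. n90/n80 = (3.250/2.810)² = 1.338 for any effect, so either value is enough and the second only confirms it.

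**Attrition convention.** SAP 6.2 does not say whether the reported n is evaluable or enrolled. In 6.1, 123 is an enrolment figure: "Planned enrollment was increased to 123 per group to protect against attrition of approximately 25% in either treatment group". Under that convention 123 × 0.75 = 92.25 evaluable, and d = sqrt(2/92.25) × 2.810 = 0.414. The range at 80% power (normal formula) is:

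| Reported total | No inflation | 15% | 20% | 25% |
|---|---|---|---|---|
| 246 | 0.358 | 0.389 | 0.401 | 0.414 |
| 300 | 0.324 | 0.352 | 0.363 | 0.375 |
| 400 | 0.281 | 0.305 | 0.314 | 0.324 |

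The last two rows also show what the third rule gives away: a report of 54 or 154 additional subjects is a report of 300 or 400.

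**Raw points.** These need an assumed SD. For d = 0.36: 0.36 × 4.06 = 1.46 points, or 0.36 × 4.73 = 1.70 points.

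**What a yes/no message would disclose.** Only the side of one threshold on which d lies: about 0.36 if n is 123 evaluable per group, or about 0.41 if n is 93.

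**The case against.** Several points on the other side stand and limit the claim.

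- A reader might infer that the sponsor recovers the treatment effect exactly. It does not. A two-sided n shows the magnitude of the standardised effect but not its sign. Points on the WOMAC scale need an SD that the report does not give, and an unstated attrition convention widens the recovered value.
- A reader might infer that giving both powers is what causes the leak, or that the sponsor is left free to choose its target between 80% and 90%. Neither follows. One n is enough, and 6.2 ties the n* trigger to 80%. What remains open is the undefined *desired* and *sufficient* power when an increase is made.
- The closing paragraph of 6.2 can be read as the operative rule. A value such as 69 per group at 90% power would then never reach the sponsor, because no increase would follow. That reading is possible, but the earlier sentence carries no such condition, so the text must be reconciled.
- The phrase about data to that point could mean conditional power. That changes the mapping: at d = 0.30 with 47 per group at the interim, n is about 160 (80%) or 214 (90%) instead of 177 or 236. The result still depends on d and can generally be inverted when an increase is needed.
- Individual allocations are not revealed. SAP 1.3 keeps subjects and investigators blinded throughout Phase I and separates treating from evaluating staff. The documents show no direct route from the sponsor's knowledge of d to biased pain scores. The risk is to the conduct and credibility of the trial; bias is not demonstrated. Nor do the documents establish that half the subjects will be in blinded follow-up at that moment, since some may not yet be enrolled.
- Any effect-based re-estimation must eventually tell the sponsor a new N. Some disclosure is inherent, and the fix reduces it without removing it.

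**Conclusion.** The concern holds as an inconsistency in the reporting rules that undoes a stated safeguard. SAP 6.2 cannot be followed as written. Under its second rule always, and under its third rule whenever an increase is made, the sponsor can work out the magnitude of the interim standardised effect. If n is reported as evaluable subjects under ordinary power, d is recovered to within about 0.01 or better. If the attrition convention is unknown, the uncertainty is about 0.04 to 0.06 SD: for 123 per group at 80% power, 0.36 to 0.41. Raw differences are conditional on an assumed SD.

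The documents do not support saying that the direction of effect or individual assignments are disclosed, or that n* has no stated power. Section 6.2 describes no banding, maximum or walled-off recipient that would blunt the disclosure. This should be corrected before the interim; it is not a flaw in the primary test itself.

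**What to change.** In SAP 6.2:

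1. Delete the sentence that reports n for 80% and 90% power.
2. Make the second and closing paragraphs state the same single message: either *continue as planned* or *increase to N*, with N taken from a short pre-specified list of steps and a stated maximum.
3. Replace *desired power* and *sufficient power* with the 80% already used for the n* trigger, and state whether N counts enrolled or evaluable subjects.
4. Keep the calculation, including the exact n*, sealed with the independent statistician until database lock.

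This costs SAP or charter wording only. The downsides are modest: a stepped N may slightly exceed the exact n*, a maximum may leave power below 80% if n* lies above it, and some coarse disclosure remains when an increase is made.
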